### Version History

Version number	Revision(s) & reason for amendment	Release date
v1.0		30.07.15
V2.0	More details provided Change in the definition of the analysis population and anthropometric indicators analysed, based on the available data Addition of sensitivity analyses, based on data limitations	20/05/2019

WorldWide Antimalarial Resistance Network (WWARN)  
[www.wwarn.org](http://www.wwarn.org)

# 1. Introduction

Malaria and malnutrition are major causes of morbidity and mortality in low and middle income countries. Annually, approximately 3.1 million under-five mortality is attributed to malnutrition. In children, the severity and extent of malnutrition is measured by various anthropometric indicators estimated from standardised growth reference curves. These metrics include wasting (low weight-for-height, a measure of acute malnutrition and the Mid-Upper Arm Circumference (MUAC) used as proxy of nutritional status in children under five years of age), stunting (low height-for-age, a measure of linear growth), and underweight (low weight-for-age, a composite of linear growth and stunting). In 2011, stunting and wasting affected at least 165 and 52 million children respectively worldwide. The relationship between malnutrition and malaria is still not clearly understood. Some studies have reported malnutrition being associated with a higher risk of malaria, others have suggested a protective effect, while other studies have shown no association at all. Similarly, the relationship between nutritional indicators and antimalarial drug efficacy has not been clearly understood with results often contrasting. The non-generalizability of these results could be due to the heterogeneity in study population, the diversity in transmission intensity, use of different growth references and different definitions, but also small sample sizes of the studies. Hence, there is a knowledge gap in association between malnutrition and antimalarial drug efficacy which needs to be addressed.

## 1.1 Aim of the study

To assess the effect of various nutritional indicators in treatment outcome in children aged 6-59 months treated with artemisinin based combination therapies for uncomplicated *P. falciparum* malaria.

## 1.2 Eligibility criteria for inclusion in pooled analysis

Studies will be deemed eligible for the purpose of this analysis if they meet the following criteria: Clinical trial including treatment with artemether-Lumefantrine (AL), artesunate-amodiaquine (AS-AQ), dihydroartemisinin-piperaquine (DP) and artesunate-mefloquine (AS-MQ) in children aged 6-59 months

- Data available on patients age, weight, gender and height at inclusion
- Minimum follow-up duration of 28 days
- Data available on treatments outcome and PCR genotyping
- Information on dose, study location is available

The data sets uploaded to the WWARN repository will be standardized using the WWARN Data Management and Statistical Analysis Plans (DMSAP v1.11) for clinical data and pooled into a single database of quality-assured individual patient data. Data will remain the property of the individual donor(s) and publication will be in accordance with an agreed publication plan.

## 1.3 Desirable Data (not required for inclusion)

- Patients mid upper arm circumference (MUAC)

- Individual patient dose data (mg/kg)
- Baseline Haemoglobin level
- Daily parasite counts (days 0, 1, 2, 3)

#### 1.4 Study Exclusion criteria

- Patients with concomitant HIV infection

#### 1.5 Patient Exclusion

The following patients (from the studies which are in the analysis) will be excluded from the analysis:

- No or missing plasmodium falciparum infection on enrolment
- Missing age and (or) weight and (or) gender
- Any of these other deviations, as defined by Clinical Module DMSAP:
  - (a) Haemoglobin < 5 g/dL on day 0
  - (b) Haematocrit < 15% on day 0

## 2. Methodologies

### 2.1 Anthropometric Indicators

Nutritional status would be assessed by using standardised age, weight, height and gender specific growth reference according to the WHO 2006 recommendations using *igrowup* Stata package. Anthropometric indicators include weight-for-age (WAZ), height-for-age (HAZ), and weight-for-height (WHZ). The nutritional status of a child will be given as a Z-score and classified as stunted, underweight or wasted as defined in the WHO guidelines.

### 2.2 Transmission Intensity

The study sites will be classified into 3 categories: low, moderate and high malaria transmission based on i) the observed PCR corrected re-infection rate and ii) the parasite prevalence estimates obtained from the Malaria Atlas Project. Other possible factors affecting re-infection rate within study, such use of bednets and post treatment prophylactic effect of long acting antimalarials will be considered when taking re-infection rate into account.

### 2.3 Conversion between haemoglobin and haematocrit

Haematocrit will be converted to haemoglobin using the following relationship:

$$\text{Hematocrit (ht)} = 5.62 + 2.60 * \text{Haemoglobin (hb)}$$

Anaemia will be defined as severe when haemoglobin concentration is below 7g/dl and as moderate if haemoglobin concentration is between 7-10g/dL

### 2.4 Dosing Calculation

The doses of artemisinin derivatives and the partner compounds received will be calculated from the number of daily tablets administered to each patient. If the daily tablet counts are not available, doses will then be back-calculated using the dosing scheme available from study protocols.

### 3. Efficacy Endpoints

**Primary:** PCR adjusted risk of *P. falciparum* recrudescence

**Secondary:** PCR adjusted risk of *P. falciparum* reinfection  
Early Parasitological response on days 1, 2 and 3

#### ***Plasmodium falciparum* recrudescence**

For the analysis of *Plasmodium falciparum* recrudescence, failure will be defined as PCR confirmed Pf recrudescence. Patients who had a new infection (of any species) will be censored at the first day the positive parasitaemia was recorded. Patients who had a reappearance of Pf parasites but the PCR result is not available will be excluded from the analysis to avoid informative censoring. Patients with recurrent parasitaemia have higher risk of recrudescence than patients in the whole population who were lost to follow-up.

#### ***Plasmodium falciparum* re-infection**

For the analysis of *Plasmodium falciparum* re-infection, failure will be defined as PCR confirmed Pf re-infection. Patients who had a new infection other than Pf species or Pf recrudescence will be censored at the first day the positive parasitaemia was recorded. Patients who had a reappearance of Pf parasites but the PCR result is not available will be excluded from the analysis to avoid informative censoring. Patients with recurrent parasitaemia have higher risk of recrudescence than patients in the whole population who were lost to follow-up.

#### ***Early Parasitological response***

A pre-defined algorithm will be used to estimate positivity status on days 2 or 3, if no observation of the blood film was recorded on that day as described in WWARN clinical Module DMSAP. For studies with frequent sampling, a patient will be classified as being positive on days 1, 2 and 3 after enrolment if the measurements within a window of  $\pm 3$  hours of 24, 48 and 72 hours were positive.

### 4. Covariates Examined

In addition to the nutritional metrics, the following variables (if available) will be examined for their association with primary and secondary treatment outcomes:

***Plasmodium falciparum* recrudescence:** Baseline parasitaemia (after log-transformation), temperature, gender, baseline haemoglobin, anaemia, gametocytes carriage on admission, patient age, transmission intensity, treatment received, treatment supervision, mg/kg dose of partner compound.

***Plasmodium falciparum* re-infection:** patient age, transmission intensity, gender, baseline temperature, baseline haemoglobin, anaemia, mg/kg dose of partner compound, treatment received and treatment supervision.

***Early Parasitological response:*** Baseline parasitaemia (after log-transformation), baseline temperature, gender, baseline haemoglobin, anaemia, gametocytes carriage on admission, patient age, transmission intensity, treatment received, treatment supervision, mg/kg dose of artemisinin derivatives.

## 5. Association between nutritional status and treatment outcome adjusted for confounders

### 5.1 Analysis Population

All patients with plausible estimates of WHZ will be included in the analysis of this measure. In the analysis of HAZ, only studies which recorded children age in months will be analysed.

### 5.2 Model building strategy

Each nutritional indicator  $a$  will be examined in a separate multivariate model as described below. Indicators will be modelled as continuous covariates and as categorical covariates (i.e using definitions from the WHO guidelines of being stunted, underweight or wasted; and using 5 categories:  $a < -3$ ;  $-3 \leq a < -2$ ;  $-2 \leq a < -1$ ;  $-1 \leq a < 0$ ;  $a \geq 0$  ).

The nutritional indicator variable(s), age and ACT treatment will be kept in the model regardless of their statistical significance. The remaining covariates will be investigated for inclusion in the model using a general strategy recommended by Collett.

- i) All possible risk factors will be examined in a univariable analysis. The log-likelihood estimates ( $-2 \times \text{Log}\hat{L}$ ) will be compared against the null model to assess if any of the variables reduce its value at 5% level of statistical significance.
- ii) All the variables identified in step (i) will be fitted together in one model and variables which are not significant in the presence of other variables based on the results of the Wald test will be identified.
- iii) A likelihood ratio test will be used to assess the impact of omitting variables identified in step (ii). If the omitted variable does not significantly impact the model log-likelihood, then it will be dropped. Only variables which led to significant change in log-likelihood will be retained.
- iv) All variables excluded from step (i) will be added to the model identified in step (iii) one by one to check if they provided any improvement to the model.
- v) A final check of the model identified in step (iv) will be carried out to ensure that none of the variables in the model could be omitted without significantly increasing the model log-likelihood, and none of the excluded variables significantly reduced the model log-likelihood.
- vi) In the final model identified in v) interaction term between ACT and anthropometric measure will be added and likelihood ratio test will be used to assess the improvement to the model.

Fractional polynomials will be used to explore the nonlinear relationships between outcome and continuous covariates.

### 5.3 Models fitted

#### PCR confirmed *Plasmodium falciparum* recrudescence/ reinfection

Risk factors for PCR confirmed recrudescence will be analysed using a Cox's proportional hazards regression with shared frailty across study sites to account for any unexplained heterogeneity.

Cox-Snell's and Martingale's residuals will be examined to assess the model fit; the underlying assumption of proportional hazards will be tested and reported when violated. The underlying assumption of proportional hazards will be tested in the final model using Schoenfeld residuals and reported when violated. For variables which violate the assumption, interaction between this variable and time intervals ( 0-28, 28-42 days) will be considered for inclusion in the final model. Same methodology will be used for the analysis of risk factors for PCR confirmed reinfection.

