### **Early Parasitological response**

Risk factors associated with persistence of parasitaemia on days 1, 2 and 3 will be assessed using mixed effects logistic regression with study site intercept fitted as a random effect.

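### The site frailty and random-intercept models can mix between-site differences into the child-level nutrition effect, and no planned analysis would show it

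*SAP*

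**What the plan says.** For recrudescence, SAP Section 5.3 specifies a Cox model with "shared frailty across study sites to account for any unexplained heterogeneity". It adds: "Same methodology will be used for the analysis of risk factors for PCR confirmed reinfection". Early parasitological response is to be analysed by "mixed effects logistic regression with study site intercept fitted as a random effect".

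Section 5.2 puts each indicator in its own model: "Indicators will be modelled as continuous covariates and as categorical covariates". On forced terms it states: "The nutritional indicator variable(s), age and ACT treatment will be kept in the model regardless of their statistical significance". Other covariates are selected on significance. At step vi an "interaction term between ACT and anthropometric measure will be added" to the final model and tested by likelihood ratio (ACT is the artemisinin-based combination received).

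Transmission intensity is the only explicitly site-level covariate. It has three levels (Section 2.2), is a candidate for all three endpoints (Section 4), and can be dropped by the selection procedure.

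Section 6 plans three sensitivity analyses: leaving out one study at a time, restricting to studies with at least three molecular markers, and imputing age. The SAP has no site-mean nutrition term, within-site centring, site stratification or fixed site effect.

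**The concern.** A shared frailty or random intercept is assumed independent of the covariates in the model. Suppose sites with lower average z-scores also differ in failure risk for reasons the covariates do not capture, such as drug resistance or quality of care. The single coefficient for the raw indicator then blends two contrasts: malnourished against well-nourished children at one site, and poorly nourished against better-nourished sites. The frailty absorbs leftover heterogeneity, but it does not remove confounding by it.

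The aim in Section 1.1 concerns how nutritional indicators affect treatment outcome in children, so the within-site contrast is the one of interest. At stake is whether an ecological association could be reported as an effect of the child's own nutritional state.

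**Working it through.** **No figure to reproduce.** The SAP states no sample size, event count or effect size. Every simulation input below is an assumption, apart from the 42-day horizon used in simulation B, which matches the time intervals in Section 5.3. In both simulations the true within-site hazard ratio (HR) is 1.00. Both use a gamma shared frailty with constant baseline hazard as a stand-in for the Cox frailty model, and neither includes further baseline covariates. The assumed correlation must therefore be read as what remains after adjustment.

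**Mechanism.** Roughly, pooled coefficient = (1 - w) x within-site slope + w x between-site slope. The between-site slope induced by confounding is rho x (SD of site log-hazard) / (SD of site-mean z).

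**Simulation A.** 60 sites x 120 children, 3% risk (60 x 120 x 0.03 = 216 events, 3.6 per site), site-mean SD 0.4, site log-hazard SD 0.8, 200 replicates.

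| Setting | Mean log HR | HR = exp(log HR) | Rejection |
|---|---|---|---|
| rho -0.5 | -0.039 | 0.96 | 10.5% |
| rho -0.5, site-mean SD 0.6 | -0.050 | 0.95 | 15.0% |
| rho -0.3 | -0.025 | 0.98 | 4.5% |
| rho -0.5, 1% risk (1.2 events per site) | -0.073 | 0.93 | 9.0% |

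In the first row the induced between-site slope is -0.5 x 0.8/0.4 = -1.0, so w is about 0.039/1.0 = 4%. At 1% risk it is 0.073/1.0 = 7%. The frailty model suppresses most of the between-site signal, but less of it when events are sparse. With the site mean added, the mean log HR lay between -0.008 and 0.009, and rejection between 2.5 and 9%.

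**Simulation B.** 40 sites x 100 children, within-site SD 1.3, rho -0.6. Site-mean SD is 0.5 and log-frailty SD 0.7 unless stated. With b the mean log HR and s its SD over replicates, rejection is approximated by Phi(-1.96 - b/s) + Phi(-1.96 + b/s).

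| Setting | Events | HR, planned model | SD of log HR | Rejection | HR, within-site term |
|---|---|---|---|---|---|
| 5% risk | 195 | 0.968 | 0.057 | 8.8% | 1.003 |
| 2% risk | 80 | 0.942 | 0.084 | 11.0% | 0.998 |
| 5% risk, SDs 0.7 and 1.0 | 194 | 0.953 | 0.058 | 13.2% | 0.993 |

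For the first row, b/s = ln(0.968)/0.057 = -0.57, and Phi(-1.39) + Phi(-2.53) = 0.082 + 0.006 = 0.088. At 2% risk with 30 to 100 children per site the HR was 0.93 to 0.95. At 20% risk it was 0.986 with 100 children per site and 0.996 with 300. At rho 0 there was no bias beyond simulation noise.

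**Interaction (true interaction HR 1.00).**

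| Setting | Planned model | Site-stratified | Within-site term, with separate site-mean x ACT term |
|---|---|---|---|
| Gradient common to all ACTs, even spread (three settings) | 0.996 to 1.004 | 0.997 to 1.005 | 0.998 to 1.006 |
| Gradient differs by ACT within sites, 190 events | 0.905 (rejection 13.5%) | 0.904 | 1.005 |
| As above, 722 events | 0.903 (41.0%) | 0.903 | 1.004 |
| One ACT per site, site size and risk differ by ACT | 0.939 (6.2%) | 0.997 | 0.997 |
| As above, rho -0.8, SDs 0.7 and 1.0 | 0.871 (10.5%) | 0.997 | 0.996 |

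Where the gradient differs by ACT, more events do not reduce the bias, and stratifying by site does not remove it.

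**The case against.** Shared frailty is a conventional multicentre choice, and the SAP cites methodological references for it. The SAP also plans adjustment: transmission intensity, treatment supervision, dose and haemoglobin or anaemia are candidates for every endpoint, baseline parasitaemia for all but reinfection, and age and ACT are forced in. These may absorb part of the confounding. That stands, although transmission is coarse, optional and no measure of poverty or drug resistance.

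A reader might infer from the Introduction that poorly nourished sites are known to do worse. The text does not say so. It offers "heterogeneity in study population, the diversity in transmission intensity", together with differing growth references and definitions and small samples, as possible reasons why earlier results disagree. The size and sign of any residual correlation are unknown, and with the opposite sign the main-effect bias would reverse.

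A reader might also infer that the interaction is contaminated simply because ACTs differ between studies. The calculations do not support that: with a common gradient and an even spread there was no bias.

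The simulated evidence has limits. With 200 replicates, 10.5% carries a Monte Carlo interval of about 6 to 15% (0.105 +/- 1.96 x sqrt(0.105 x 0.895/200)). Rejection after the split still reached 9% in one setting of simulation A, so the gain in false positives is not clear everywhere. The logistic model was not simulated; it shares the independence assumption, but the size there is unmeasured.

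None of this supplies an analysis that separates the two contrasts. Leaving out one study at a time detects influential studies, but each refit still blends both.

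**Conclusion.** The concern holds as a conditional one. The planned models rest on an independence assumption that the SAP neither checks nor relaxes. If it fails, the main effect is modestly biased: HR about 0.93 to 0.97 per z-score and roughly 9 to 15% false positives, under an assumed site correlation of -0.5 to -0.6 and few events per site. In simulation B's 5% risk setting the bias is a little over half a standard error. False positives were not inflated at -0.3, and the bias nearly vanishes when events per site are many.

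The ACT interaction is biased only if the between-site nutrition gradient differs by ACT, or if ACTs are spread over sites that differ in size or risk. The SAP pools four ACTs and rules out neither.

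The documents do not support the stronger statement that the planned estimate will be biased. They do support adding a check, because the issue bears on the study's aim and would otherwise go unseen.

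**What to change.** Add to Section 6 a refit of each final continuous-indicator model, both the Cox frailty models and the logistic model for early response:

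- Enter the child's deviation from the site mean and the site mean as separate terms.
- For step vi, give each of the two terms its own ACT interaction.
- Base child-level conclusions on the within-site terms where they differ from the pooled coefficient.
- For categorical indicators, where a deviation from the mean is not defined, add the site proportions: one for each WHO-defined binary, four for the five-category version.
- Use a Cox model stratified by site only as a check on the main effect. A reader might take it as an equivalent alternative, but it left the interaction HR at 0.90 when the gradient differed by ACT.

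The cost is a few lines of text, a few more model terms and somewhat wider intervals. In simulation B the SD of the main-effect log HR rose by at most about 2% (0.086/0.084 = 1.02). That of the interaction rose by about 4 to 15% (0.112/0.108 = 1.04; 0.120/0.104 = 1.15). The cost for the categorical and logistic models was not calculated.

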### **Early Parasitological response**

Risk factors associated with persistence of parasitaemia on days 1, 2 and 3 will be assessed using mixed effects logistic regression with study site intercept fitted as a random effect.

## **6. Sensitivity analyses**

In the sensitivity analysis, the final models, will be refitted

- with each study's data excluded, one at a time

Coefficient of variation around the parameter estimates will be calculated.

Exclusion of studies will identify any influential studies, that is, studies with unusual results (due to variations in methodology, patient population, or other reasons) that affect the overall pooled analysis findings

- in studies which used at least three molecular markers to distinguish recrudescence from the reinfection;
- using multiple imputations for age in studies which have not provided age in months, or in which majority of children had age given as integer (see section 6.1. for more details)

### **6.1 Multiple imputations**

For studies with age measured in years for all or majority of children (>50%), multiple univariable imputation for such values will be conducted using an interval regression imputation method (Stata command: *mi impute intreg* ), assuming for a child with recorded age of x years that their true age is between x years 0 months and x years 11 months.

All variables assessed in the multivariable models: weight, height, sex, study site anaemia, fever,  $\log_{10}$  parasitaemia, ACT, transmission intensity area will be included as auxiliary variables in the imputation model, as well as parasite positivity on day 2, recrudescence by day 42, new infection by day 42, day of outcome, and cumulative hazard (Nelson-Aalen estimator) for recrudescence and for new infection. Twenty datasets will be imputed.

For each imputed dataset, anthropometric measures will be re-estimated using the imputed age. Final models will be re-fitted on the 20 imputed datasets and final overall model coefficients and standard errors will be estimated, adjusted for the variability between imputations (stata command: *mi estimate*) according to the combination rules by Rubin.

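### The age imputation lets a child recorded as 0 years be drawn below the plan's own 6-month limit, which biases those infants' HAZ and WAZ upward in the sensitivity analysis

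*SAP*

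**What the plan says.** The aim in SAP section 1.1 concerns "treatment outcome in children aged 6-59 months treated with artemisinin based combination therapies", and the eligibility criteria in section 1.2 repeat the range: "artesunate-mefloquine (AS-MQ) in children aged 6-59 months".

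Section 6 plans a sensitivity analysis that imputes age for studies without age in months, or with mostly integer ages. Section 6.1 does this by interval regression with 20 imputed datasets. The interval for a child recorded as x years is that "their true age is between x years 0 months and x years 11 months", with no exception for x = 0. The predictors begin with "All variables assessed in the multivariable models: weight, height, sex, study site anaemia, fever" and also include outcome variables. In each dataset, "anthropometric measures will be re-estimated using the imputed age", and the final models are refitted.

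Section 1.5 excludes patients whose age is missing. Nothing in the SAP drops or bounds an imputed age below 6 months. Section 5.1 limits the main HAZ analysis to studies with age in months.

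**The concern.** An eligible child recorded as 0 years is at least 6 months old, so about half of the interval given to that child cannot contain the true age. In interval-regression imputation the bounds are the only hard limit on a draw. Height and weight move the predicted age but do not bar values below 6 months.

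The error has one direction. With height and weight fixed, a younger age raises HAZ and WAZ, and averaging over 20 imputations does not remove a one-sided error. The classes in section 5.2 are 1 Z wide between −3 and 0, so a shift of a sizeable fraction of a Z moves infants across classes and across the stunting and underweight cut-offs. Age is also forced into every model, so the adjustment variable carries the same error.

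This sensitivity analysis is the only place where studies with age in years can contribute to HAZ. It is therefore the plan's check on whether leaving them out matters. If the infants in it are misclassified, agreement or disagreement with the main HAZ result is harder to interpret.

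**Working it through.** **Step 1: the interval against the age range.** The stated rule gives 12x to 12x + 11 months.

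| Recorded years x | Interval (months) | Within 6–59? |
|---|---|---|
| 0 | 0–11 | No |
| 1 | 12–23 | Yes |
| 2 | 24–35 | Yes |
| 3 | 36–47 | Yes |
| 4 | 48–59 | Yes |

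Only x = 0 conflicts. On a continuous scale 6 of its 11 months lie below the limit (6/11 = 55%); counted in completed months it is 6 of 12.

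**Step 2: how many draws fall below 6 months.** The documents give no prediction error for age, so these inputs are assumptions: predicted age m = 7 to 10 months, residual SD s = 2 to 3 months. The draws are normal, truncated to 0–11:

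P(age < 6) = [Φ((6−m)/s) − Φ((0−m)/s)] / [Φ((11−m)/s) − Φ((0−m)/s)]

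- m = 7, s = 3: (0.3694 − 0.0098) / (0.9088 − 0.0098) = 0.400.
- m = 10, s = 2: 0.0228 / 0.6915 = 0.033.

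**Step 3: the average age error.** This is the mean of the normal truncated to 6–11 minus its mean when truncated to 0–11. Each mean is m + s[φ(α) − φ(β)] / [Φ(β) − Φ(α)], where α and β are the standardised lower and upper bounds.

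**Step 4: the HAZ error.** Assumed growth is 1.3 to 2 cm per month and assumed length SD is 2.2 cm, so HAZ error = age shift × growth / 2.2.

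| m | s | P(age < 6) | Mean with 0–11 | Mean with 6–11 | Shift (months) | HAZ error (Z) |
|---|---|---|---|---|---|---|
| 7 | 2 | 0.32 | 6.89 | 7.89 | 1.00 | 0.6–0.9 |
| 7 | 3 | 0.40 | 6.54 | 8.19 | 1.65 | 1.0–1.5 |
| 8 | 2 | 0.17 | 7.72 | 8.29 | 0.57 | 0.3–0.5 |
| 8 | 3 | 0.30 | 7.17 | 8.39 | 1.22 | 0.7–1.1 |
| 9 | 2 | 0.08 | 8.43 | 8.71 | 0.28 | 0.2–0.3 |
| 9 | 3 | 0.21 | 7.73 | 8.61 | 0.87 | 0.5–0.8 |
| 10 | 2 | 0.03 | 8.98 | 9.11 | 0.13 | 0.1 |
| 10 | 3 | 0.14 | 8.21 | 8.81 | 0.60 | 0.4–0.5 |

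The extremes are 0.13 × 1.3 / 2.2 = 0.08 and 1.65 × 2 / 2.2 = 1.50, hence about 0.1 to 1.5 Z. With 12 instead of 11 months as the upper bound in both intervals, the ranges barely move (3–38% of draws; shift 0.12–1.66 months).

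**The case against.** **Reach.** The rule is used in one sensitivity analysis, for studies where most ages are in years, and there only for infants recorded as 0. An infant whose age is in months is not imputed. The SAP gives no count, so there may be none or many. This stands and limits the importance of the point, but it does not remove the contradiction.

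**Size.** A reader might infer that these infants' HAZ and WAZ are grossly overstated. An age 3 months too low would raise HAZ by 3 × 1.3 / 2.2 = 1.8 to 3 × 2 / 2.2 = 2.7 Z. But the 3 months is a chosen figure, and under the assumptions above 60–97% of draws are not below 6 months. A simulation that imputed from height and weight alone, under assumed growth curves, gave residual SDs of about 6–8 months and mean HAZ errors of 1.1–1.7 Z. Section 6.1 lists many more predictors, and the documents supply neither growth curves nor residual SDs, so they do not support a large error as a general statement.

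**Upper limit.** A reader might also infer that the rule cuts off the last month of each year of life. The wording reads naturally as completed months. It becomes a cut only if coded as a continuous bound at 12x + 11, which the SAP does not say. It needs clarifying but is not an established error.

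**Younger enrolled infants.** Section 1.2 does not say that source trials enrolled only the 6–59 month range. If one also enrolled younger infants, a child recorded as 0 could truly be under 6 months, and a 6-month floor would make that child too old. Such a child is outside the stated population, so the floor remains right for eligible children. What stands is that age in whole years cannot establish eligibility, and the plan should flag this.

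**Conclusion.** The point holds as an internal contradiction with a known direction: at x = 0 the imputation interval ignores the SAP's own 6-month limit, and every draw below it biases HAZ and WAZ upward. It concerns only infants recorded as 0 years in the section 6.1 analysis. WHZ is indexed on height, so its values do not change, and the main HAZ analysis does not use imputed ages.

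The size is conditional. Mean HAZ in these infants is overstated by about 0.1–1.5 Z if the assumed predicted ages, residual SD, growth rate and length SD apply. The top of the range needs the lowest predicted age, the larger SD and the fastest growth together; with predicted age 10 and SD 2 the effect is close to nil. The same assumptions do not yield a figure for WAZ, only its direction. The effect on the pooled estimates cannot be judged without the number of such infants. The correction is worth making because it is cheap and the check it protects is the only use of year-only studies for HAZ.

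**What to change.** In section 6.1:

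- For x = 0, set the lower bound at 6 months, or at the contributing study's minimum enrolment age if that is higher.
- Keep all other intervals within 6–59 months.
- State that the upper limit is in completed months, so the continuous bound is just below 12(x + 1) months.
- Where a contributing study enrolled infants under 6 months and recorded age only in years, flag that the eligibility of children recorded as 0 cannot be verified. Report their number.

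The cost is about one line of SAP wording and two bound variables in the imputation code, plus a count for the flagged studies. No other analysis changes.

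### The age-imputation model in SAP 6.1 has no ACT-by-outcome terms, so an ACT-by-nutrition interaction refitted on imputed ages is partly attenuated for HAZ and, less so, WAZ

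*SAP*

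**What the plan says.** Section 5.2, step (vi), comes after covariate selection: "interaction term between ACT and anthropometric measure will be added and likelihood ratio test will be used to assess the improvement to the model". Section 6 then opens its list of checks with "In the sensitivity analysis, the final models, will be refitted", and one of those checks uses multiple imputation for age.

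Section 6.1 gives the imputation method: "multiple univariable imputation for such values will be conducted using an interval regression imputation method". For a recorded age of x years it assumes that "their true age is between x years 0 months and x years 11 months". The covariates are listed one by one. On treatment, the list ends with "ACT, transmission intensity area will be included as auxiliary variables in the imputation model". On outcome, it names parasite positivity on day 2 and then "recrudescence by day 42, new infection by day 42, day of outcome, and cumulative hazard (Nelson-Aalen estimator) for recrudescence and for new infection". No product of ACT with an outcome or hazard is named, and no imputation by ACT. The indices are recalculated from each imputed age. The section then states: "Final models will be re-fitted on the 20 imputed datasets and final overall model coefficients and standard errors will be estimated", with the results combined by Rubin's rules.

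Section 5.1 limits the main HAZ analysis to studies that recorded age in months. Imputed ages therefore enter HAZ only through this sensitivity analysis.

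**The concern.** An imputation model should be at least as rich as the model fitted to the imputed data. The plan accepts this in part, since it puts the outcomes and Nelson-Aalen hazards into the age model. It does not extend it to the one interaction that the analysis model tests.

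With separate terms only, the relation between age and outcome, given the other covariates, is forced to be the same for every ACT. HAZ and WAZ recomputed from those ages then under-represent any real ACT difference. This sensitivity analysis is the only route by which year-only studies contribute to HAZ. A smaller interaction there could be put down to the added studies or to coarse ages when the imputation model had caused part of it.

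**Working it through.** **No figure to reproduce.** The SAP gives no sample size, effect size or share of year-only ages on this point. The check is an algebraic argument followed by simulation under stated assumptions.

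**Why ACT terms are needed.** Let the analysis model have log hazard β1·z + β2·ACT + β3·z·ACT, with z the index, d the event indicator and H the cumulative hazard. To first order, the outcome informs z through (β1 + β3·ACT)·(d − H). If β3 is not zero, the imputation model needs ACT·d and ACT·H as well as d and H. The list in 6.1 has d, H and ACT, but not the products.

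**Measures.** With g the fitted interaction:
- loss = 1 − g(imputed) / g(true age)
- share recovered = [g(fix) − g(main)] / [g(true age) − g(main)]

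**Simulation 1, logistic, HAZ.** Assumptions: 6,000 children aged 6-59 months, two ACTs with log OR 0 and −0.4 per z-score, 10% risk, an assumed growth curve, 30-40 replicates, 5 imputations, Monte Carlo SE about 0.01.

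| Children imputed | True age | As in 6.1 | By ACT | By ACT within recorded year |
|---|---|---|---|---|
| 20% | −0.401 | −0.368 | −0.382 | −0.396 |
| 40% | −0.394 | −0.327 | −0.357 | −0.379 |
| 70% | −0.411 | −0.305 | −0.352 | −0.391 |

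- Total loss: 0.033/0.401 = 8%, 0.067/0.394 = 17%, 0.106/0.411 = 26%.
- Recovered by ACT: 0.014/0.033 = 42%, 0.030/0.067 = 45%, 0.047/0.106 = 44%. As a share of the true-age interaction this is 3.5, 7.6 and 11.4 percentage points.
- Recovered by ACT within recorded year: 0.028/0.033 = 85%, 0.052/0.067 = 78%, 0.086/0.106 = 81%.

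**Simulation 2, Cox, the SAP's model type.** Assumptions: 12,000 children, log HR −0.3 and 0 per z-score, event risk about 6%, HAZ SD 1.3, a smooth growth curve, 25 replicates, 10 imputations, parameter uncertainty in the imputation ignored. The product terms are ACT by event, hazard and time.

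| Index, ages in years | True age | As in 6.1 | With products | Share kept: 6.1, then products |
|---|---|---|---|---|
| HAZ, 25% | 0.308 | 0.279 | 0.294 | 0.91, 0.95 |
| HAZ, 50% | 0.284 | 0.233 | 0.258 | 0.82, 0.91 |
| HAZ, 100% | 0.311 | 0.216 | 0.258 | 0.69, 0.83 |
| WAZ, 25% | 0.294 | 0.283 | 0.287 | 0.96, 0.97 |
| WAZ, 50% | 0.291 | 0.269 | 0.277 | 0.92, 0.95 |
| WAZ, 100% | 0.312 | 0.270 | 0.292 | 0.87, 0.94 |

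- Total loss: HAZ 9%, 18%, 31%; WAZ 4%, 8%, 13%.
- The paired HAZ differences from true age are −0.029, −0.051 and −0.095 (SE 0.003-0.005). With products they are −0.015, −0.026 and −0.053. Recovered: 14/29 = 48%, 25/51 = 49%, 42/95 = 44%.
- In percentage points, the products recover 4, 9 and 14 for HAZ and 1, 3 and 7 for WAZ.
- At 50%, the HAZ effects close in from both sides: −0.299 to −0.265 in one ACT, −0.015 to −0.032 in the other.

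**The remaining loss.** The age model is linear with normal errors, while the z-score is nonlinear in age. Imputing within recorded year relaxes that linearity and recovers most of what imputing by ACT alone leaves.

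**No true interaction.** A smaller Cox run (10 replicates, half of ages in years, log HR −0.15 in both ACTs) gave an interaction of −0.013 with true age and −0.010 imputed.

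**The case against.** The strongest reply is about scope. Step (vi) adds the interaction to a model already called final at step (v), and the SAP does not say that a significant interaction is carried into section 6. Nor does 6.1 fix the functional form: it lists variables without excluding products. The aim in section 1.1 poses no ACT-specific question, and only one of the sensitivity analyses is touched. All of this stands. The point is therefore conditional on the interaction being retained or tested on the imputed data, and it takes the covariate list in its plain sense.

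Three stronger readings are tempting and are not supported:

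- A reader might infer that imputed ages carry no ACT difference at all. They carry most of it: with every age imputed, 69% of the HAZ interaction and 87% of the WAZ interaction remained, because recorded year, height and weight hold much of the information.
- A reader might attribute the whole loss to the missing ACT terms. Adding them, or imputing by ACT, recovered at most about half of the HAZ loss.
- A reader might infer that an ACT with no nutrition effect acquires a meaningful one, or that a true interaction would be declared non-robust. The spurious effects in simulation 1 were −0.006, −0.015 and −0.028 on the log odds scale (at most OR 0.97), against a Monte Carlo SE of about 0.01. No power, interval or decision rate was computed, so a change of conclusion has not been shown.

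**Conclusion.** The point holds as a minor one. Following 6.1 as listed, with the step (vi) interaction retained or tested on the imputed data, attenuates a true ACT difference by about 8-31% in total for HAZ and 4-13% for WAZ. The part due to the missing ACT terms is about 4-14 percentage points for HAZ, slightly under half to half of the loss. The rest is attributed to the linear normal age model.

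These sizes rest on assumed growth curves, effect sizes, event risks, two equally sized ACT groups and assumed shares of year-only ages from 20% to 100%. The loss grows with that share. The direction agreed across both simulations. The main HAZ analysis uses no imputed ages, WHZ is built from weight and height alone, and no false interaction was seen where none existed.

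**What to change.** Add to section 6.1 that, whenever the refitted model contains or tests the ACT-by-nutrition interaction, age is imputed separately by ACT, and within recorded year of age where numbers allow. That version recovered about 78-85% of the HAZ loss. For ACT groups too small for this, add ACT-by-outcome and ACT-by-cumulative-hazard terms to the common imputation model, which recovers about half. State in 5.2 or 6 whether an interaction retained at step (vi) belongs to the final models that are refitted.

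The cost is one option or a few product terms in the imputation command. The downside is less stable imputation in small ACT or age strata.
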